### 9.3 Schedule of Events

#### 9.3.1 Overview

The study will comprise three phases:

1. A pre-treatment screening/observation phase
2. A treatment phase of 1 week with panobinostat only (Arm A), pegylated IFN- $\alpha$ 2a only (Arm C) or the combination of panobinostat and pegylated IFN- $\alpha$ 2a (Arm B).
3. A post-treatment observation period of three weeks.

A graphical overview of the study is given in Figure 1. A summary of all study procedures at each visit is provided in Table 1. Time windows and blood draws for each study visit are also listed in Table 1.

#### 9.3.2 Screening/pre-entry phase

Once a candidate for study entry has been identified, the patient will be scheduled to meet with a study representative to discuss the study. If the patient decides to participate, s/he will sign the IRB-approved consent form. Subsequently, the participant will have a screening visit; this visit can occur immediately after signing the consent form.

During this screening visit (V1), the patient will be questioned regarding their medical history and will have laboratory testing performed to determine eligibility for the study. The following procedures will be performed:

- Obtain a medical history, including all information relevant to inclusion and exclusion criteria
- Review concomitant medications
- Perform a complete physical exam, including a non-mydriatic fundoscopic eye exam
- Perform a 12-lead ECG to calculate QTc intervals
- Schedule patient for a cardiac stress echocardiogram test (unless data already available)
- Obtain samples for screening laboratory tests:
  - Plasma HIV-1 RNA testing by Roche Taqman Version 2.0 assay.
  - CD4 T cell counts.
  - HIV antibody (if not previously documented).
  - TSH levels.
  - Urine HCG pregnancy test for female participants of childbearing potential.
  - PPD skin test or T spot TB test (unless data already available).
  - Hematology parameters and chemistry parameters as per Table 1.

If the candidate is eligible for the trial, he or she will return for one pre-entry visit. At this visit (V2), the following procedures will be performed:

[figure not shown]
- Pregnancy test (women of childbearing age).
- Other lab tests as indicated in Table 1.
- Collection of blood/serum for virological and immunological and gene expression assays.
- Immunogenetic studies for HLA class I and IL-28B genotyping.
- Record baseline level of diarrhea, nausea and vomiting that patients experience with their regular antiretroviral regimen.

Time	Screening/Pre-Entry		Treatment Phase				Post-Treatment Observation	
	≤-30d †	≤-10d †	D0 (0h)	D0 (6h)	D2	*D4 (6h)	D10	D28
Windows						+1	+/- 2	+/- 2
Amount Collected from Blood Draws (cc)	49	91	60	57		87	99	87
IFN- $\alpha$ 2a injection (Arm B and C only)			X					
Panobinostat (Arm A and B only)			X		X	X		
Visit numbers	V1	V2	V3			V4	V5	V6
Phone call for evaluation of AEs					X			
CBC 	X	X	X			X	X	X
HLA, KIR, IL-28b GT		X						
Liver function tests 	X					X		X
Chemistry 	X	X				X	X	X
TSH	X							
Pregnancy testing 	X	X	X					X
Hep B/C serologies, PPD/TB Spot PT, PTT	X							
Eye exam	X		X					
Stress echocardiogram/dobutamine stress test	X							
HIV antibody	X							
Differential blood count and CD4/CD8 T cell counts	X	X	X			X	X	X
Plasma HIV-1 RNA	X		X	X		X	X	X
Complete/targeted physical exam	X	X	X			X	X	X
Panobinostat PK			X	X		X	X	
ECG	X		X	X		X		
Histone acetylation levels		X	X	X		X	X	X
HIV-1 DNA		X	X			X	X	X
Viral outgrowth assays		X					X	
CD4 T cell -associated HIV-1 RNA		X	X	X		X	X	X
HIV-1 DNA in CD4 T cell subsets		X					X	
Immune phenotyping		X	X	X		X	X	X
Functional immune assays		X		X		X	X	
Gene expression profiling		X					X	

Immune activation markers		X		X		X	X	

Table 1: Schedule of events during the study. (*blood draws on this day will occur 6h after administration of study drug). CBC includes WBC, RBC, PLT, Hgb, Hct, MCV, MCH, RDW, MCHC, MPV. Liver function tests include AST/ALT, TBili, DBili, Albumin. Chemistry levels include Na, K, Cl, HCO3, BUN, Crea, Glucose, Mg. Women of childbearing potential only. †Number reflects time interval during which study visit should occur from Study Entry.
								

## Protocol

**Figure 1:** Study overview. PBT refers to panobinostat.

### 9.3.3 Treatment phase

Study entry will be defined as the day on which the first dose of study drug is administered (day=0, visit V3).

On this day, participants will have the following procedures performed:

- Perform a pregnancy test, ECG and vital signs/physical exam (including eye exam), as described in pre-treatment assessment (9.2.4).
- Review concomitant medications.
- Collect blood for baseline immunologic and virologic assays.
- Perform randomization to treatment Arm A or B or C.
- After the above procedures are completed, administer one s.c. dose of PEG-IFN- $\alpha$ 2a in patients randomized to treatment Arm B and C.
- Immediately after the first administration of PEG-IFN- $\alpha$ 2a, participants will be asked to take the first pill of panobinostat p.o., at the stage-specific dose if randomized to arm A or B.
- At 6h after administration of panobinostat, blood samples will be collected for virological, immunological and pharmacokinetic assays.
- 4-6 hours after administration of panobinostat, at the time of Cmax for panobinostat, a 12-lead ECG will be performed.
- On discharge, participants randomized to stage A or B will receive two more stage-specific panobinostat doses and will be instructed to take them in the mornings of study day 2 and day 4.

On Day 2, participants will be called by phone by one of the study investigators to discuss possible side effects. Participants will return on Day 4, six hours after administration of the third dose of panobinostat (visit V4), for collection of blood samples for virological, immunological and gene expression studies, as described in Table 1, and for an ECG. The full volume of blood to be collected on day 4 will only be collected if the most recently available hemoglobin level is  $\geq 12.0$  g/dL for men and hemoglobin  $\geq 11.0$  g/dL for women.

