### 5.3.2 Pharmacokinetics (PK)

Panobinostat is rapidly absorbed with a median Cmax reached within 1 h after oral administration. The absolute oral bioavailability of panobinostat is approximately 30%. The compound can be administered

regardless of food intake as the variability and overall systemic exposure remained unchanged in participants taking panobinostat with or without food. AUC increased linearly and proportionally with doses up to 50 mg. The inter-individual variability (CV%) in systemic exposure is 60%. The plasma protein binding of panobinostat (mainly to albumin) is moderate (89.6% at 37°C) and independent of concentration. Elimination half-lives averaged 15 hours. Steady state is achieved by the third dose following days 1, 3, and 5 (TIW) weekly (QW) dosing. The metabolism of panobinostat involves several metabolic pathways including reduction, hydrolysis, oxidation, and glucuronidation processes. It is a substrate of cytochrome P450 3A4 (CYP3A4) with minor involvement of CYP2D6 and 2C19 as well as a weak inhibitor of CYP2D6 in vivo. Panobinostat and its metabolites (~at least 40 metabolites in circulating plasma) were nearly equally excreted in urine and bile/feces of participants. Dose adjustments are not necessary in patients with severe renal impairment.

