#### 5.4.3.4 Pharmacokinetics

Plasma levels of panobinostat increased in all 15 participants of the CLEAR study with the highest levels measured two hours after dosing as compared to eight hours after the previous dose, consistent with a Cmax occurring approximately 1-2 hours after oral ingestion as described previously. There was no clinical or laboratory evidence for relevant pharmacological interactions between panobinostat and the antiretroviral drugs used in this study (NRTIs, PIs, NNRTIs).

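### The day-0 ECG that section 9.3.3 places at panobinostat Cmax falls 2-5 h after the Cmax given elsewhere in the protocol, and no other scheduled ECG falls at Cmax

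*Combined protocol and SAP*

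**What the plan says.** Section 9.3.3 gives both the time of the day-0 post-dose ECG and the reason for it: "4-6 hours after administration of panobinostat, at the time of C max for panobinostat, a 12-lead ECG will be performed". Table 1 places this ECG in the 6 h column for day 0, beside the pharmacokinetic sample.

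Two other sections give the time of Cmax:

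- Section 5.3.2 says that median Cmax is "reached within 1 h after oral administration".
- Section 5.4.3.4, on the earlier single-group panobinostat study in HIV, describes a Cmax "occurring approximately 1-2 hours after oral ingestion as described previously". The highest levels in that study were measured two hours after dosing.

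The only other post-dose ECG is on day 4, and section 9.3.3 fixes its time: "Participants will return on Day 4, six hours after administration of the third dose of panobinostat". Between these two visits there is a telephone call on day 2. For the second and third doses, participants "will be instructed to take them in the mornings of study day 2 and day 4".

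**The concern.** The protocol treats QTc prolongation as a risk to be monitored. Section 5.3.5 reports significant QTc abnormalities, including one case of Torsades de pointes, with intravenous dosing on consecutive days. Table 4 makes QTc findings a reason to stop dosing, with final decisions discussed with the study chairs.

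Doses fall on days 0, 2 and 4. Day 2 has no ECG, and the day-4 ECG follows the last dose. The day-0 post-dose ECG is therefore the only scheduled one that can change whether the second and third doses are taken. An investigator who relies on section 9.3.3 would read a normal tracing at 4-6 h as reassurance at peak exposure. By the protocol's own pharmacokinetics it is not at the peak.

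**Working it through.** **1. Can a Cmax at 4-6 h be reproduced?** No. Section 5.3.2 gives 1 h or less (median) and section 5.4.3.4 gives about 1-2 h. No section gives 4-6 h or reconciles the figures.

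**2. How late is the ECG?** Lateness = ECG time minus time of Cmax, with Cmax at 1-2 h.

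- Smallest: 4 - 2 = 2 h.
- Largest: 6 - 1 = 5 h.
- At the 6 h shown in Table 1: 6 - 2 = 4 h to 6 - 1 = 5 h.

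If the peak comes before 1 h, which section 5.3.2 allows, the upper end slightly exceeds 5 h.

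**3. Does another ECG cover Cmax?** Table 1 and section 9.3.3 schedule ECGs at screening, on day 0 before dosing, on day 0 at 4-6 h, and on day 4 at 6 h after the third dose. None is 1-2 h after a dose.

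**4. How far has the level fallen by then?** Section 5.3.2 says: "Elimination half-lives averaged 15 hours". The documents give no concentration curve, so I assume one compartment and a peak no later than 2 h in each person. The level relative to peak is then 2^(-gap/15), where gap is hours since the peak.

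| Time of peak | Level at 2 h | Level at 4 h | Level at 6 h |
|---|---|---|---|
| 0.5 h | 0.933 | 0.851 | 0.776 |
| 1 h | 0.955 | 0.871 | 0.794 |
| 2 h | 1.000 | 0.912 | 0.831 |

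With a peak at 1-2 h, the level at the planned ECG is 79-91% of peak (79-83% at 6 h). At 2 h, the late edge of a 1-2 h window, it is 95-100%. For any peak up to 2 h, the level at 2 h is 2^(2/15) = 1.10 times that at 4 h and 2^(4/15) = 1.20 times that at 6 h.

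This is small beside the 60% between-person coefficient of variation in exposure stated in section 5.3.2. A distribution phase, which the documents do not describe, would make the fall larger.

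**5. How many treatment courses are affected?** Panobinostat slots in Arms A and B: (2 + 6) + (2 + 6) + (4 + 10) = 30. These are slots, not necessarily different people, because section 7.3 lets stage 1 and 2 participants enter stage 3. Arm C takes no panobinostat.

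**The case against.** The strongest reply is that what is shown is a wrong clause, not a gap in monitoring. Deleting the reference to Cmax would remove the contradiction, and no section establishes that Cmax is the right time to look for QTc change. Much of this stands. A reader might infer that the planned ECG misses the largest QTc effect. The documents do not support that, because they say nothing about when the effect peaks. They equally give no delayed effect as a reason for 4-6 h. The only reason they give is Cmax. Deleting the clause would make the text consistent but leave what the trial does unchanged, with no tracing at the target that the authors set.

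A second reply is that the exposure difference is small and modelled. That stands too. Nothing here is expressed in milliseconds, or as a chance of missing a Table 4 threshold. In the same model, with doses 48 h apart, the third dose carries an accumulation factor of 1 + 2^(-3.2) + 2^(-6.4) = 1.12. The day-4 level at 6 h is then 0.794 to 0.831 times 1.12, or about 89-93% of the first-dose peak. The schedule therefore does take an ECG near first-dose peak exposure, but after the last dose, when it can no longer affect dosing.

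A third reply is that other safeguards exist. QTc must be below 450 msec (men) or 470 msec (women) before dosing, and potassium and magnesium must not be low (section 9.2.4). Regular QT-prolonging drugs are excluded (section 7.2.22). The first dose is observed in hospital (section 8.5), and section 11.4.4 expects little clinically important prolongation at low doses. These limit the consequence, but they do not supply the tracing at Cmax.

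**Conclusion.** The inconsistency is real and lies in the current text. The day-0 post-dose ECG is 2-5 h late for its stated target, taking Cmax at 1-2 h, and no scheduled ECG falls at Cmax. That conclusion needs only the times in the protocol and no model.

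The practical consequence is modest. The exposure figures rest on the assumed one-compartment decline and a peak by 2 h in every person, whereas section 5.3.2 gives only a median time. It would go too far to conclude that QTc monitoring fails, or that any dosing decision would change. The point is worth acting on because this tracing is the one that can inform the second and third doses, and the repair is cheap.

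**What to change.** In section 9.3.3 and Table 1, take the day-0 Cmax ECG in Arms A and B at 1-2 h after panobinostat, citing section 5.4.3.4. A fixed 2 h time justified by section 5.3.2 would not do, because that section puts the median peak within 1 h. Remove the description of Cmax from any ECG kept at 4-6 h. The day-4 ECG can stay at 6 h.

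Keeping the 4-6 h ECG as a second tracing is optional. It would preserve the pairing with the 6 h sample ("At 6h after administration of panobinostat, blood samples will be collected for virological, immunological and pharmacokinetic assays") and the match to the day-4 ECG, and it would cover a delayed effect if there is one. It costs one short tracing per treatment slot, 30 in all, during a hospital stay that already runs to the 6 h blood draw, plus a Table 1 column or footnote. No new visit is needed.

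If only one tracing is kept, it should be the one at 1-2 h. There is then no extra tracing, and the small loss is the pairing with the 6 h pharmacokinetic sample and the match to day 4. The protocol states no concentration-QTc analysis that depends on that pairing.

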## Protocol

### 9.3.4 Post-treatment observation period

Participants will return for additional collection of blood samples for virological and immunological analyses on day 10 (visit V5) and 28 (visit V6) (see Table 1). Preceding each blood collection, the hemoglobin levels determined from the visit before (visit V4 and V5, respectively) will be used to assess the participant's ability to give blood. A minimum requirement of hemoglobin  $\geq 12.0$  g/dL for men and hemoglobin  $\geq 11.0$  g/dL for women will be used.

### 9.4 Long-term follow-up

All participants will be encouraged to follow-up with their primary HIV care providers after completion of this study, and to actively participate in age-appropriate screening exams recommended by the US Preventative Services Task Force (USPSTF, <http://www.uspreventiveservicestaskforce.org>). All participants will be entered into a study registry where they will be contacted once a year (by phone or in person) for 10 years after completion of their study participation to determine if any diseases that may be attributable to the study medication have occurred.

### 9.5 Early termination visit

Any participant who discontinues study treatment prematurely should be encouraged to continue to participate in all scheduled visits.

A participant may voluntarily discontinue participation in this study at any time. The investigator may also, at his or her discretion, discontinue the participant from participating in this study at any time. If a participant is prematurely discontinued from participation in the study for any reason, the investigator must make every effort to perform the following evaluations:

- Perform clinical evaluation.
- Review adverse events and concomitant medications.
- Obtain samples for laboratory tests:
  - Hematology (CBC/differential), Chemistry testing.
  - HIV RNA testing by Roche Taqman Version 2.0 assay.
  - CD4 T cell counts.
  - Collection of blood samples for virological and immunological assays.

### 9.6 Pregnancy

Women of childbearing potential will be required to have a negative urine pregnancy test prior to first study drug administration. Any woman who becomes pregnant during the study period will not receive any further study medication and will be followed for safety until the end of the study or until the outcome of the pregnancy, whichever is longer. The participant will be advised to have her infant undergo regular doctor's visits for 6 months following birth in order to assess and record any abnormal health outcomes.

In addition, if the participant continues her pregnancy, the patient is encouraged to prospectively register her pregnancy in the "Antiretroviral Pregnancy Registry" (In US and Canada: [name], international: [contact]).

## **10.0 STUDY MONITORING**

### 10.1 Internal Safety Review Committee (ISRC)

This committee will consist of the following four individuals: [name], [name] (study co-chairs), [name] (protocol clinician) and [name] (protocol statistician).

## Protocol

The committee will meet by conference call every month during the trial or at an appropriate interval based on the pace of enrollment. A **quorum** of **three** Committee members is required for each scheduled meeting, teleconference or unscheduled meeting. A project manager will be responsible for tabulating all adverse events, distributing these tables to the members of the Internal Safety Review Committee and organizing the meetings.

The committee will review all adverse events that occur during the trial. The Internal Safety Review Committee will be responsible for forwarding the following reports to the Safety Monitoring Committee for immediate review:

- a. Serious adverse events.
- b. Grade 3 and 4 adverse events that are related to the study medication.
- c. CD4 T cell count decline to <50% of relative CD4 cell count compared to baseline (average of the screening and pre-entry visits) that is not attributable to non-adherence with antiretroviral medication.

### 10.2 Safety Monitoring Committee (SMC)

This committee will consist of the following three individuals: [name] (chair), [name] (member) and [name] (statistician).

A **quorum** of **all three** Committee members is required at scheduled meetings, teleconferences or unscheduled meetings. All members will have signed a Confidentiality Agreement. In addition, members will treat the reports, meeting discussions, minutes and recommendations of the SMC as confidential.

The committee will meet to review safety information at scheduled meetings two times per year during the study. Unscheduled meetings will be convened in case of serious adverse events or grade 4 toxicity events that are attributable to the study medication.

### 10.3 Definitions of Adverse Reactions

#### 10.3.1 Adverse event (AE)

An AE is any untoward medical occurrence in a patient or clinical investigation participant that occurs after providing written informed consent for participation in a study. Therefore, an AE may or may not be temporally or causally associated with the use of a medicinal (investigational) product or other protocol-imposed intervention. An AE can therefore be any unfavorable and unintended sign (including an abnormal laboratory finding), symptom, or disease temporally associated with the use of a medicinal (investigational) product or other protocol-imposed intervention, regardless of attribution.

An AE **does** include:

- Exacerbation of a pre-existing illness.
- An increase in frequency or intensity of a pre-existing episodic event or condition.
- A condition detected or diagnosed after study drug administration even though it may have been present prior to the start of the study.
- Continuous, persistent disease or symptoms present at baseline that worsen following the start of the study.
- Overdose of either study drug or concurrent medication, even when not associated with any signs or symptoms.
- Complications that occur as a result of protocol-mandated interventions (e.g. invasive procedures such as cardiac catheterizations).

## Protocol

An AE **does not** include:

- Pregnancy
- A medical or surgical procedure (e.g. surgery, endoscopy, tooth extraction, transfusion); the condition that leads to the procedure may be an AE.
- A pre-existing disease or condition present or detected at the start of the study that does not worsen.
- Situations where an untoward medical occurrence has not occurred (e.g. hospitalizations for cosmetic elective surgery, social and/or convenience admissions).
- The disease/disorder being studied, or expected progression, signs, or symptoms of the disease/disorder being studied, unless more severe than expected for the participant's condition.

AEs may include pre- or post-treatment events that occur as a result of protocol-mandated procedures (e.g. invasive procedures, modification of participant's previous therapeutic regimen). Intercurrent illnesses that occur after screening but before starting treatment, and that are not the result of protocol-mandated procedures, do not need to be captured as AEs.

### 10.3.2 Serious Adverse Event (SAE)

An SAE is any untoward medical occurrence that at any dose:

- Results in death.
- Is life-threatening. Any adverse event that places the participant, in the view of the investigator, at immediate risk of death from the reaction as it occurred (i.e. it does not include a reaction that, had it occurred in a more serious form, might have caused death).
- Requires in-patient hospitalization or prolongation of existing hospitalization.
- Results in persistent or significant disability or incapacity.
- Is a congenital anomaly/birth defect.
- Is an event that required intervention to prevent permanent impairment or damage.
- Important medical events that do not result in death, are not life-threatening, or do not require hospitalization may be considered serious adverse events when, if based upon appropriate medical judgment, might jeopardize the participant and might require medical or surgical intervention to prevent one of the outcomes listed above.

## 10.4 Monitoring for Adverse Events

### 10.4.1 Recording of Adverse Events

The occurrence of adverse events should be sought by non-directive questioning of the participant at each visit during the study. Adverse events also may be detected when they are volunteered by the participant during or between visits or through physical examination, laboratory test, or other assessments.

Each reported AE or SAE will be described by its duration (i.e. start and end dates), suspected relationship to the study drugs, and grade of seriousness.

At each visit, the participant will have an opportunity to spontaneously mention any new medical problems. The investigator should inquire about adverse events by asking one of the following standard questions:

“Have you had any (other) medical problems since the last visit?”

